19.0 UNSCHEDULED VISITS

The minimum acceptable frequency of participant visits and the monitoring clinical laboratory values is specified in Section 18.0 Study Assessments by Visit and Schedule of Study Evaluations and Procedures: Washout Through Follow-Up (Appendix A). Additional visits and/or clinical laboratory tests to monitor toxicity will be performed as indicated and their frequency will depend on concurrent medical condition(s) and concomitant medication use.

20.0 PATIENTS LOST TO FOLLOW-UP

If a participant misses a visit and is not responding to telephone calls (all attempts to contact the patient will be documented), more concerted action in locating the patient will be taken. At least two attempts will be made to contact the patient by telephone and two additional attempts to contact the patient's emergency contact if this information is available. If these attempts are not successful, then a registered letter will be sent to the last known address of the participant. If this is unsuccessful, then the participant will be considered lost to follow-up and discontinued from the study.

21.0 ADVERSE EVENTS

21.1 Definitions

21.1.1 Adverse Event (AE)

An adverse event (AE) is defined as any untoward medical occurrence in a clinical investigation subject administered a pharmaceutical product, which does not necessarily have a causal relationship with this treatment. An adverse event can therefore be any unfavorable and/or unintended sign (including an abnormal laboratory finding), symptom, or disease temporally associated with the use of an investigational medicinal product, whether or not related to the investigational medicinal product. All adverse events, including observed or volunteered problems, complaints, or symptoms will be recorded.

Adverse events include:

- A clinical event occurring from the time a participant provides written informed consent and before ixazomib is initiated on study day 1.
- Onset of a clinical event after ixazomib is initiated on study day 1.
- An increase in the frequency, severity, and/or seriousness of a preexisting condition during the study, including scleroderma.
- Worsening of preexisting condition leading to over overnight hospitalization will be reported as a serious adverse event (SAE).

Wherever possible, a specific disease or syndrome rather than individual associated signs and symptoms will be identified and recorded. However, if an observed or reported sign or symptom is not considered a component of a specific disease or syndrome, it will be recorded as a separate adverse event.

Adverse events will not include:

- Events identified at screening visit that meet exclusion criteria
- Medical or surgical procedures (e.g., surgery, endoscopy, tooth extraction, or transfusion); a condition leading to the medical or surgical procedure will be recorded as the adverse event, not the procedure itself.
- Situations where an untoward medical occurrence has not taken place. Examples may include:
 - Hospitalizations planned for a pre-existing condition which has not worsened
 - Hospitalizations that occur for treatment procedures not due to an AE or SAE.
 - Hospitalizations for a diagnostic procedure where the hospitalization does not routinely require overnight stay.
 - Overdose or misuse of ixazomib or any concomitant therapy that does not result in any adverse signs or symptoms

For laboratory safety measurements, any instances of absolute values being outside the reference range or changes at any visit after study start that are considered as clinically significant will be recorded as AEs. In addition, at the investigator's discretion, any changes or trends over time in laboratory measurements can be recorded as AEs if such changes or trends are considered to be clinically relevant, even if the absolute values are within the reference range.

Laboratory abnormalities or other abnormal clinical findings will be reported as an adverse event if any of the following are applicable:

- If an intervention is required as a result of the abnormality
- If action with study drug ixazomib is taken to reduce or interrupt its dosing as a result of the abnormality
- Based on the clinical judgment of the Investigator

Clinically significant abnormal laboratory values occurring during the clinical study will be followed until repeat tests return to normal, stabilize, or are no longer clinically significant.

Laboratory results will not be reported as AEs in the following cases:

- Laboratory measurements already outside the reference range at screening, unless a further increase / decrease is considered an exacerbation of a pre-existing condition.
- Abnormal laboratory results caused by mechanical or physical influences on the blood sample (e.g., in vitro hemolysis) and flagged as such by the laboratory in the laboratory report.
- An abnormal laboratory value that cannot be confirmed after repeat analysis (i.e., the previous result could be marked as not valid and will not necessarily be reported as an AE).

21.1.2 Serious Adverse Event (SAE)

An adverse event is considered serious if, in the view of the investigator it results in any of the following outcomes:

- Death.

The SAE event must be the cause of death to meet this criterion.

- A life-threatening adverse event.

An adverse event is considered “life-threatening” if, in the view of the investigator its occurrence places the subject at immediate risk of death. It does not include an event that, had it occurred in a more severe form, might have caused death.

- Requires in-hospitalization or prolongation of existing hospitalization.

Any hospital admission with at least 1 overnight stay will be considered an in-patient hospitalization. An emergency room or urgent care visit without hospital admission will not be recorded as an SAE under this criterion, nor will hospitalization for a procedure scheduled or planned before signing of informed consent, or elective treatment of a pre-existing condition that did not worsen from baseline. However, unexpected complications and/or prolongation of hospitalization that occur during elective surgery or procedure will be recorded as adverse events and assessed for seriousness. Worsening of a pre-existing condition leading to hospitalization will be reported as an SAE. Admission to the hospital for social or situational reasons (i.e., no place to stay, live too far away to come for hospital visits, respite care) will not be considered an inpatient hospitalization.

- A persistent or significant disability/incapacity or substantial disruption of the ability to conduct normal life functions.
- A congenital anomaly/birth defect.
- An important medical event.

Important medical events that do not meet any of the above criteria may be an SAE when, based upon appropriate medical judgment, they may jeopardize the participant and may require medical or surgical intervention to prevent one of the outcomes listed above as an SAE criterion.

Adverse events that do not fall into the above categories are defined as nonserious AEs.

21.2 Assessment of Adverse Events

The severity (intensity) of each adverse event will be assessed as mild, moderate, or severe, and each adverse event will be categorized as to its potential relationship to the study drug ixazomib using the categories of yes or no.

21.2.1 Severity Assessment

The severity of each AE (i.e., nonserious and serious) will be assessed as follows:

- **Mild severity:** A type of AE that is usually transient, easily tolerated, causing minimal discomfort not generally interfering with usual activities of daily living, and may require only minimal treatment or therapeutic intervention.
- **Moderate severity:** A type of AE that is sufficiently discomforting so as to interfere with usual activities of daily living and is usually alleviated with additional specific therapeutic intervention.
- **Severe severity:** A type of AE that is incapacitating with inability to work or perform usual activities of daily living, or significantly affects clinical status, and may require intensive therapeutic intervention.

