 1. Ixazomib administration will be revised to the first reduction dose of 3 mg and should follow the dose cycle schedule for the remainder of that study visit with weekly monitoring of alkaline phosphatase, total and indirect bilirubin, and AST or ALT for the remainder of that study cycle until the next study visit. The 3 mg dose should follow the dose cycle schedule for the remainder of that study visit and subsequent study visits unless worsening of liver function tests is observed.
- If serum alkaline phosphatase is greater than 2 X upper limited of normal (ULN), total bilirubin is greater than 1.5 X ULN except in patients with predominantly unconjugated hyperbilirubinemia (e.g., Gilbert's syndrome), and AST or ALT is more than 2 X ULN, ixazomib dose will be managed as follows:
 1. Ixazomib administration will be discontinued. The participant will be monitored weekly until the liver function tests return to baseline or resolve. The participant will be discontinued from the study and will proceed to complete assessments and procedures for early discontinuation (See 15.0 Early Discontinuation).

9.2.3.4 If other nonhematologic adverse events, grade 2 or 3, ixazomib dose will be managed as follows:

1. Ixazomib administration will be interrupted and paused until the adverse event has improved to grade 1 or resolved.

2. Supportive care for the adverse event may be considered as clinically indicated.
3. Upon improvement of the adverse event to grade 1 or resolution, ixazomib administration may resume at the first reduction dose of 3 mg and should follow the dose cycle schedule for the remainder of that study visit and subsequent study visits unless a recurrent adverse event grade 2 or 3 of the same nature occurs.
4. In that instance, ixazomib administration will be interrupted and paused until the adverse event has improved to grade 1 or resolved.
5. Upon improvement of the adverse event to grade 1 or resolution, ixazomib administration may resume at the second reduction dose of 2.3 mg and should follow the dose cycle schedule for the remainder of that study visit and subsequent study visits unless a recurrent adverse event grade 2 or 3 of the same nature occurs.

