- All other serious (non-fatal/non-life-threatening) events within 4 calendar days of the sponsor-investigator's observation or awareness of the event

See below for contact information for the reporting of SAEs to Takeda Pharmacovigilance.

The sponsor-investigator must fax or email the SAE Form per the timelines above. A sample of an SAE Form will be provided.

The SAE report must include at minimum:

- Event term(s)
- Serious criteria
- Intensity of the event(s): Sponsor-investigator's or sub-investigator's determination. Intensity for each SAE, including any lab abnormalities, will be determined by using the NCI CTCAE version specified in the protocol, as a guideline, whenever possible. The criteria are available online at <http://ctep.cancer.gov/reporting/ctc.html>.
- Causality of the event(s): Sponsor-investigator's or sub-investigator's determination of the relationship of the event(s) to study drug administration.

Follow-up information on the SAE may be requested by Takeda.

Intensity for each SAE, including any lab abnormalities, will be determined by using the NCI CTCAE version used at your institution, as a guideline, whenever possible. The criteria are available online at <http://ctep.cancer.gov/reporting/ctc.html>.

In the event that this is a multisite study, the sponsor-investigator is responsible to ensure that the SAE reports are sent to Takeda Pharmacovigilance (or designee) from all sites participating in the study. Sub-investigators must report all SAEs to the sponsor-investigator so that the sponsor-investigator can meet his/her foregoing reporting obligations to the required regulatory agencies and to Takeda Pharmacovigilance, unless otherwise agreed between the sponsor-investigator and sub-investigator(s).

Relationship to all study drugs for each SAE will be determined by the investigator or sub-investigator by responding yes or no to the question: Is there a reasonable possibility that the AE is associated with the study drug(s)?

Sponsor-investigator must also provide Takeda Pharmacovigilance with a copy of all communications with applicable regulatory authorities related to the study product(s), as soon as possible but no later than 4 calendar days of such communication.

SAE and Pregnancy Reporting Contact Information

[REDACTED]
[REDACTED]

Suggested Reporting Form:

- SAE Report Form (provided by Takeda)
- US FDA MedWatch 3500A:
[REDACTED]
- Any other form deemed appropriate by the sponsor-investigator

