24.5 Safety Analyses

The safety population will be used for the analysis of safety data. Summaries of AEs, deaths, and patient disposition will be presented, comparing patients in the two treatment groups. Study periods will be comprised of the following:

- Entire 24-week study period
- First 12 weeks of treatment
- Subsequent 12 weeks of treatment

Safety measurements will include the following:

- Treatment-emergent AEs
- Treatment-emergent SAEs
- Treatment-emergent treatment-related AEs
- Treatment-emergent treatment-related SAEs
- Treatment-emergent AEs leading to ixazomib dose modifications
- Treatment-emergent AEs leading to early discontinuation of ixazomib
- Treatment-emergent changes in clinical laboratory measures
- Treatment-emergent changes in patient vital signs
- Treatment-emergent changes in UCLA SCTC GIT 2.0 questionnaire

AEs will be mapped to system organ classes and preferred terms in MedDRA. Treatment emergent events are defined as those that start or worsen after the start of study treatment through 28 days after the last dose of study treatment. AEs will be summarized by treatment group, system organ class, and preferred term, and by event severity and the event's relationship to study treatment. At each level of summation, patients will be counted only once, under the greatest severity and strongest study-drug relationship.

Clinical laboratory data will be summarized at each measurement time point and for each patient's final post-baseline measurement in the following ways:

- (1) with descriptive statistics (mean, standard deviation, median, and range) for each

measurement time point;

(2) with descriptive statistics for the change from baseline in the measurements at each post-baseline time point; and

(3) with tables summarizing the frequencies of patients below, within, and above the normal ranges at each time point as compared with baseline. All clinical laboratory values collected during the study will be listed, with values outside the normal ranges flagged for clinical evaluation. Grade 3 and 4 laboratory results will be listed and summarized.

Vital signs will be summarized by group and listed by patient.

Data from the UCLA SCTC GIT 2.0 questionnaire at each assessment time will be summarized descriptively without imputation for missing values.

Concomitant medications will be summarized by treatment group based on mapping to drugclasses and generic terms in the WHO Drug Dictionary.

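### The AE severity scale has no laboratory criterion, so an asymptomatic count that interrupts dosing can be tabulated as mild or severe depending on the assessor, and no CTCAE version is fixed where grades are used

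*Combined protocol and SAP*

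**What the plan says.** Section 21.2 sets one rule for all events: "The severity (intensity) of each adverse event will be assessed as mild, moderate, or severe". Section 21.2.1 makes the scope explicit: "The severity of each AE (i.e., nonserious and serious) will be assessed as follows". Mild is described as "A type of AE that is usually transient, easily tolerated, causing minimal discomfort not generally interfering with usual activities of daily living", and the definition goes on to allow for minimal treatment. Moderate is an event "sufficiently discomforting so as to interfere with usual activities of daily living", usually relieved by some specific intervention. Severe covers incapacity, or a marked effect on the patient's clinical state, with intensive intervention possible. None of the three definitions mentions a laboratory value or an action taken with the study drug.

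Other sections use numeric grades:

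- Section 23.1, on SAE reports to the drug supplier, sets intensity (laboratory abnormalities included) by the "NCI CTCAE version specified in the protocol" and, a little later, by the "NCI CTCAE version used at your institution". No version is named in the text available.
- Section 24.5 states: "Grade 3 and 4 laboratory results will be listed and summarized". Section 25.5.1 repeats this for the extension. Neither names the scale.
- Section 9.2.3.4 begins "If other nonhematologic adverse events, grade 2 or 3", and the neuropathy and rash rules in 9.2.3 also use grades. The scale is again not named.

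Sections 24.5 and 25.5.1 tabulate AEs by severity and count each patient once, under the greatest severity.

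**The concern.** Safety and tolerability are the primary objective (section 6.1), and severity is one of the planned ways to summarise AEs. The protocol expects thrombocytopenia and leukopenia (section 5.0). It also names hematologic and hepatic effects as areas where ixazomib and MMF overlap, which is the reason for comparing the two background groups. These toxicities are often found on a blood test before the patient feels anything, so a scale built on tolerability and daily function serves them poorly.

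If the severity category for such an event rests on the assessor's reading rather than on the count, the AE-by-severity table can show the same platelet value at opposite ends of the scale in two patients. It can also disagree with the laboratory-grade summary of the same event. For a serious event, sections 21.2.1 and 23.1 each prescribe a severity, on different scales.

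**Working it through.** The plan states no figure on this point, and no hypothesis test is planned (section 24.2). The check is therefore to follow one event through the text.

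1. **The event.** Section 9.2.2.2 pauses ixazomib at a platelet count at or below 30,000 and expressly includes asymptomatic cases. Section 9.2.2.1 pauses it at an ANC at or below 1000, on the count alone.
2. **Is it an AE?** Yes. Section 21.1.1 makes a laboratory abnormality an AE when it leads to the study drug being reduced or interrupted.
3. **Which category?** Section 21.2.1 must supply one.
   - *Moderate* requires discomfort that interferes with daily activities. An asymptomatic count does not meet this as worded.
   - *Mild* is open. The event causes no discomfort and does not limit activity, and nothing excludes an event that interrupts dosing.
   - *Severe* is also open, through the clause on clinical state, but only by judgement and with no threshold.
4. **Where does it go?** Into the AE-by-severity tables of 24.5 and 25.5.1, in either category.

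The scales in use, side by side:

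| Section | What is graded | Scale named | Levels mentioned |
|---|---|---|---|
| 21.2.1 | every AE, serious or not | the protocol's own | mild, moderate, severe |
| 23.1 | SAE intensity, including laboratory abnormalities | NCI CTCAE, two version references, none specified | not listed |
| 24.5, 25.5.1 | laboratory results | none | grades 3 and 4 |
| 9.2.3 | neuropathy, rash, other nonhematologic AEs | none | grades 1 to 3 |

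Two inconsistencies follow. A serious AE is covered by both 21.2.1 and 23.1, on different scales. The laboratory summaries in 24.5 and 25.5.1 use a fourth grade that 21.2.1 does not have, so they must rest on some other scale, which is not stated.

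**Size, for scale only.** Planned enrolment is 12, with 6 in each background group (section 7.1). One patient moved between categories changes a row by 1/12 = 8.3 percentage points overall, or 1/6 = 16.7 points within a group. Because each patient is counted once under the greatest severity, the shift appears only in rows where this event is that patient's worst.

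**The case against.** The case for leaving the plan alone has real substance.

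- **The scale is not purely symptomatic.** All three levels also weigh the intervention needed, and severe has a route that does not depend on symptoms. A count that brings a dose pause and daily blood tests need not be called mild. This stands, and it means the result depends on the assessor. A reader might infer that the scale will give a falsely mild picture, but the text shows only that it can.
- **The events do not disappear.** Section 24.5 plans laboratory summaries by visit, shift tables, a listing of all values, a grade 3 and 4 summary, and counts of AEs leading to dose modification or discontinuation. Section 24.4 counts dose changes. This also stands and confines the problem to the severity tables. The grade 3 and 4 summary is a weaker safeguard than it looks, because its scale is not named.
- **Section 9.2.3 may not conflict.** In the neuropathy and rash rules, grades 1 to 3 are labelled with the same three words as 21.2.1. A reader might infer that CTCAE is used across the protocol and clashes with 21.2.1 everywhere. It is named only in 23.1, so the documents do not support that. What remains in 9.2.3 is an unnamed scale.
- **Section 23.1 serves a different purpose.** It governs reports to the supplier, uses CTCAE as a guide, and does not define an analysis table. That is correct, but 21.2.1 also covers serious events, so the overlap is real.

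A reader might also infer that the severity results could not be compared with other ixazomib data. The documents do not say how other studies graded AEs, so that claim is not made here.

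**Conclusion.** The point holds within limits. For asymptomatic laboratory toxicities that interrupt dosing, section 21.2.1 does not determine a severity category: moderate is ruled out as worded, and mild and severe are both available. SAE intensity has two rules and no fixed CTCAE version, and the laboratory grades in 24.5 and 25.5.1 have no named source.

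The consequence is confined to the AE-by-severity tables. The 8.3 and 16.7 points show what one patient weighs in a study of this size and are not an estimated bias. The conclusion assumes that at least one participant has such a count without symptoms. The protocol foresees this but gives no expected frequency. The hematologic dosing rules use numeric counts, so the severity label does not alter how those events are managed. The plan should be changed because the remedy is cheap and the output serves the primary objective, but the safety analysis does not fail without it.

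**What to change.** Name one NCI CTCAE version in section 21.2.1 and cite the same version in 23.1, replacing both current references. Grade AEs by it: ideally all of them, and at minimum the laboratory AEs, using the recorded values. Produce the severity tables and the laboratory-grade summaries in 24.5 and 25.5.1 on that scale, and say so there. If the three-level scale is kept for clinical AEs, state which scale each table uses, and give one rule for serious events.

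The unnamed grades in 9.2.3 need to be reconciled with the chosen scale by the sponsor. Those grades drive dose management, so this comment proposes no dose rule and takes no position on the thresholds.

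The cost is protocol and CRF wording and a little regrading. Laboratory AEs already recorded can be regraded from stored values, with no new visits or samples.

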21.2.2 Causality Assessment

The relationship of an adverse event to the administration of the study drug ixazomib will be assessed according to the following definitions:

- **No** (unrelated, not related, unlikely to be related) – The time course between the administration of ixazomib and the occurrence or worsening of the adverse event rules out a causal relationship and another cause (concomitant drugs, therapies, complications) is suspected.
- **Yes** (possibly, probably, or definitely related) – The time course between the administration of ixazomib and the occurrence or worsening of the adverse event is consistent with a causal relationship and no other cause (concomitant drugs, therapies, complications) can be identified.

The definition implies a reasonable possibility of a causal relationship between the event and the study drug ixazomib. This means that there are facts (evidence) or arguments to suggest a causal relationship.

The following factors will also be considered in assessing causality:

- Temporal sequence from ixazomib administration:
The adverse event should occur after the study drug ixazomib was initiated on study day 1. The length of time from ixazomib exposure to the event will be evaluated in the clinical context of the event. Treatment-emergent adverse events will be captured in relation to the ixazomib dose, the need for dose reduction or interruption, and any recurrence of the AE upon re-initiation of ixazomib as permitted per the protocol.
- Preexisting and concomitant illnesses:
Each AE and SAE will be evaluated in the context of the natural history and course of the scleroderma being treated and any other illness, pre-existing or new, the participant is experiencing.
- Concomitant drugs:
Other drugs the participant is taking or the treatment the participant receives will be evaluated to determine whether any of them might be recognized to cause the event in question.
- Known response pattern for this class of study drug:
Clinical and/or preclinical data may indicate whether a particular response is likely to be a class effect.

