been studied when given concurrently with MMF. Therefore, the primary objective of this study is to assess the safety and tolerability of ixazomib alone and when administered concurrently with MMF. MMF has a safety profile that overlaps with the safety profile of ixazomib, particularly in regards to hematologic, gastrointestinal, and liver effects, and peripheral edema. In addition, the safety profiles may overlap in other ways which are not foreseen. The present safety and tolerability study incorporating careful safety monitoring will aid in assessing the potential significance of any overlap in the safety profiles of ixazomib and MMF.

As well, there are potentially important differences between multiple myeloma and scleroderma-ILD patient populations regarding both demographics and comorbidities. Ixazomib is approved for treatment of multiple myeloma in combination with lenalidomide and dexamethasone in patients who have received at least one prior therapy. Multiple myeloma is somewhat more common in men than women (1.4:1). It is an illness of older adults having a median age at diagnosis of 66 years; only 10% of patients are younger than age 50 years, and only 2 % are younger than 40 years [146]. Compared with myeloma patients, the scleroderma-ILD population is younger with the diagnosis of scleroderma most often occurring between the ages of 30 and 50 years, and more predominantly in women. A case series of 60 scleroderma patients demonstrated that 28 % had clinical and/or electrophysiological evidence of peripheral neuropathy [147]. Those with peripheral neuropathy were more likely to be male, African American, to have diabetes mellitus, to manifest anti-U1 RNP scleroderma autoantibody, and to have the limited cutaneous form of systemic scleroderma which is not eligible for this study. As well, a potential non-scleroderma etiology for the peripheral neuropathy such as diabetes mellitus was identified in 82.3% of those scleroderma patients.

Should ixazomib administered alone or concurrently with MMF be demonstrated to have an acceptable safety and tolerance profile in patients with SSc-ILD, this study may offer insights important to the design of subsequent clinical trials evaluating ixazomib as a therapeutic alternative or addition to existing therapies for this serious illness

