10.0 BACKGROUND MEDICATION MMF

The study will enroll participants who either are not on background SSc-ILD medication or are on a background stable dose of MMF (see Study Population 8.1.2 SSc and SSc-ILD Related Criteria). MMF will be treated as background medication and will continue to be prescribed as part of usual clinical care. MMF will not be provided as part of the study. Participants on MMF will continue to take MMF during the study. Background MMF cannot be switched to another agent, nor is the addition of other background medications permitted; if this is necessary, the patient will be discontinued from the study and will proceed to complete early discontinuation assessments and procedures. Changes in the dose of the background MMF are not planned during the study; but if patient management requires a dose adjustment within the established limits of MMF ≤ 1.5 g BID, the patient will remain in the study. Changes within the allowable dose range of MMF will not be considered a deviation. MMF can produce significant adverse effects, including effects on the GI system, skin, liver, and central nervous system. Participants will be monitored for adverse effects of MMF when being used concurrently with ixazomib.

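### The yes/no causality definitions in 21.2.2 do not cover an adverse event with compatible timing and an identified other cause, and the Yes condition is stricter than its own label and the SAE question in 23.1

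*Combined protocol and SAP*

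**What the plan says.** All references are to the combined protocol and SAP.

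- **21.2** allows two answers only: "each adverse event will be categorized as to its potential relationship to the study drug ixazomib using the categories of yes or no".
- **21.2.2, No** applies when the timing "rules out a causal relationship and another cause (concomitant drugs, therapies, complications) is suspected". Its label runs from unrelated to unlikely to be related.
- **21.2.2, Yes** applies when the timing "is consistent with a causal relationship and no other cause (concomitant drugs, therapies, complications) can be identified". Its label is "possibly, probably, or definitely related".
- **21.2.2, explanatory text** then adds: "The definition implies a reasonable possibility of a causal relationship between the event and the study drug ixazomib". It asks for evidence or argument pointing to causality and does not require other causes to be excluded. Timing, other illness, concomitant drugs and class pattern are listed as further factors to weigh.
- **23.1** sets a yes/no question for each SAE reported to the supplier ("Is there a reasonable possibility that the AE is associated with the study drug(s") and attaches no condition about other causes.
- **16.1, 24.5 and 25.5.1** list treatment-related AEs and treatment-related SAEs among the safety measures. 24.5 and 25.5.1 also tabulate AEs by relationship and compare the two groups, which 25.5.1 identifies as participants with and without background MMF.
- **5.0** states: "MMF has a safety profile that overlaps with the safety profile of ixazomib, particularly in regards to hematologic, gastrointestinal, and liver effects". **10.0** adds: "MMF can produce significant adverse effects, including effects on the GI system, skin, liver, and central nervous system".

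**The concern.** A two-category classification should give every event exactly one answer. Here each definition joins two conditions, and the two sets of conditions are not complements. An event can have timing that fits ixazomib and also have another cause that the assessor can name. Such an event fails No because of its timing and fails Yes because of the other cause.

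The section also carries more than one standard. The operative sentence for Yes excludes any event with another identifiable cause. The label, the explanatory text and the 23.1 question do not. Two careful assessors could answer differently for the same event, and one assessor could give two answers for the same SAE depending on the form.

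Safety and tolerability is the primary objective, and 5.0 frames it as ixazomib alone and with MMF. The treatment-related columns are where a reader will look for what ixazomib adds. MMF can be named as the other cause only in the group that takes it, so the wording could bear unequally on the two groups.

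**Working it through.** The plan states no figure on this point, so there is none to reproduce. The check is a cross-tabulation of the two definitions, followed by a comparison with the other texts.

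**Step 1. Apply the operative sentences literally.** Timing has two levels. Other cause has three, because No speaks of a cause that is suspected and Yes of one that can be identified.

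| Timing | No other cause suspected | Suspected, not identified | Identified |
|---|---|---|---|
| Compatible with ixazomib | Yes | Yes | **neither** |
| Rules ixazomib out | neither | No | No |

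The lower-left cell is empty on a literal reading but harmless: every text in the section points to No. In the upper-right cell the texts disagree. The table shows where the gap lies. Its cells are not equally likely, so it says nothing about how often the gap is met.

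**Step 2. Put the upper-right cell to each text**, for an event where ixazomib remains a reasonable possibility.

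| Text | Answer |
|---|---|
| Yes sentence, 21.2.2 | fails |
| No sentence, 21.2.2 | fails |
| Yes label, 21.2.2 | Yes (possibly related) |
| Explanatory text, 21.2.2 | Yes |
| SAE question, 23.1 | Yes |

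The listed factors do not settle it. They tell the assessor to look for other drugs and illnesses that could explain the event, but no rule says which category follows when one is found.

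**Step 3. Trace where the call is used.** In each of the lists in 16.1, 24.5 and 25.5.1, 2 of the 9 measures use it (treatment-related AEs and treatment-related SAEs), and 9 − 2 = 7 do not. It also feeds the tables by relationship, and unrelated status enters the follow-up rule for non-serious AEs in 21.4.

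**Step 4. Sensitivity to one patient.** With 6 participants planned per group, moving one patient changes a group's percentage by 100 × 1/6 = 16.7 points. A patient is counted once, at the strongest relationship, so this happens only if that patient has no other related event at the same level of the table. This is the effect of one reclassification, not an estimate of how many would occur.

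**The case against.** The strongest reply is that the labels already divide all events: unlikely or unrelated on one side, possibly or more on the other. An assessor who uses the labels, the explanatory text and the listed factors will reach a sensible answer, and the explanatory text uses the same reasonable-possibility phrase as 23.1. This largely stands. A reader might infer that the treatment-related summaries are undetermined, or that the Yes sentence contradicts the explanatory text. The documents do not support either. A workable standard is present, and the Yes sentence is narrower than that standard: an event that meets it also has a reasonable possibility. What remains is that 21.2.2 tells assessors to apply the definitions, and the definitions state a different standard from the label.

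A second reply concerns exposure. Only an identified cause falls in the gap. Overlapping toxicity makes MMF hard to separate from ixazomib, so MMF may often be merely suspected, which still gives Yes. An MMF dose stable for 3 months before Day 1 (8.1.2) and the baseline symptom inventory (18.2) make MMF a less likely cause of some new events. It is also arguable whether the underlying disease counts as an other cause, since the parenthesis in the definitions names drugs, therapies and complications. This stands too. A reader might infer that the 6 MMF participants, or all 12 participants, measure the size of the problem; those counts show only where another cause could arise.

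Third, the consequences are limited. There is no formal hypothesis testing (24.2). AEs, SAEs, discontinuations and laboratory changes are summarized whatever the causality call. Under 23.1, SAEs from first dose to 30 days after the last dose go to the supplier whatever the call; later ones turn on relatedness, for which 23.1 has its own question. In a small open-label study without a control, relatedness stays a matter of judgement under any wording.

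**Conclusion.** The point holds as a defect in a stated rule, and the wording should be corrected. The operative definitions leave one foreseeable kind of event unclassified. The Yes condition is inconsistent with its own label and narrower than both the explanatory text and the 23.1 question. Assessors who follow the label will be consistent with 23.1; those who follow the sentence will not. The likely results are inconsistent classification or under-recording of related events in 2 of the 9 safety measures and in the tables by relationship.

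A reader might go further and infer that related events will be under-counted in the MMF group. The documents do not show that. They allow it, because MMF can be the identified cause in that group only, but they give no rate for such events and no indication of which sentence assessors follow. Neither frequency nor direction can be computed. The conclusion rests on reading the definitions as written and on the distinction the text itself draws between a suspected and an identified cause.

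**What to change.** Replace both definitions in 21.2.2 with the question already in 23.1, made exhaustive:

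- **Yes:** there is a reasonable possibility that the event is associated with ixazomib.
- **No:** there is not.

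State that another identified cause does not by itself make the answer No. Keep timing, other illness, concomitant drugs and class pattern as guidance for that single question. Use one answer for the study tables and the SAE report.

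**Cost.** The change is to protocol wording, and to the case report form if it repeats the definitions (the form is not in the documents). It needs no new visits, patients or data. Two downsides should be accepted openly. More events may be classed as related, so that column will separate less from all-cause events. AEs already classed need one documented re-read, with the initial call kept on record and any changes listed, because a re-read in an open-label study could itself introduce bias.
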